2 INTRODUCTION: BACKGROUND INFORMATION AND SCIENTIFIC RATIONALE

2.1 Background Information

Periodontitis is among the most prevalent causes of years lived with disability among adults worldwide (GDB Collaborators 2020). Periodontitis is a bacterial inflammatory disease that has been reported to affect nearly 40% of Americans aged 30 years or older (GDB Collaborators 2020). If left untreated, periodontitis can lead to tooth loss and patient-perceived morbidity (Eke et al. 2018). Historically, antibiotic use has been an integral part of periodontal disease treatment. However, antibiotic stewardship calls for optimizing antibiotic prescribing to effectively treat infections, reduce antibiotic misuse, and prevent the development of antibiotic-resistant microbial strains (Dinsbach 2012, Doron & Davidson 2011, Sabtu et al. 2015). Since 2015, the American Dental Association (ADA) developed evidence-based guidelines limiting circumstances for prophylactic antibiotic use in dental practice (Sollecito et al. 2015, Lockhart et al. 2019); however, evidence regarding antibiotic use in the treatment of periodontal infections is considered weak because of substantial inconsistencies across small scale trials (Smiley et al. 2015). Further, existing trials are underpowered to assess the effects of disease- and patient-related factors to adjunctive antibiotic benefit, therefore, dentists are left to decide when adjunctive antibiotics are indicated, and which dental patients need them to achieve periodontal health (Smiley et al. 2015). In the context of periodontitis treatment, a biological rationale exists to support adjunctive antibiotic use to reduce periodontal pathogenic bacteria, but clinical trials assessing adjunctive antibiotic effectiveness have presented varying results depending on the study, sample population and disease characteristics (Hafajee et al. 2003, Hafajee et al. 2007, Teughels et al. 2020). Nonetheless, data from academic studies suggest that adjunctive systemic antibiotics may be beneficial for certain populations only, as the biological response to treatment is highly variable across individuals (Smiley et al. 2015). This marked variability warrants the identification of person and/or diseaserelated characteristics that are linked to maximum benefit from adjunctive antibiotic treatment. Consequently, guidelines may be established with tailored indications for their use with the goal of minimizing antibiotic misuse in periodontal treatment to avoid development of antibiotic resistance while optimizing outcomes (Garcia et al. 2013).

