To address limitations in evidence pertaining to adjunctive antibiotic use as part of NSPT, the study objective is to assess the effectiveness of systemic AMXM combination antibiotics as an adjunct to SRP (AMXM group) vs. SRP alone (Placebo group) in periodontal patients with Stages II-III, Grade A-C periodontitis who receive care in clinical practices within the National Dental PBRN. In brief, patient participants in

the AMXM group will receive a loading dose of Amoxicillin 500mg and Metronidazole 500mg followed by a self-administered dose (500mg) of the two drugs every 8 hours (qh8) for 10 days. This regimen was employed in a recent periodontitis clinical trial of forty-two adult patient participants and demonstrated a high safety profile with no drug-related adverse events (Ramón Gómez-Sandoval et al. 2020). Additionally, the present study will include effect modification analyses for sample subpopulations of interest, such as smokers versus non-smokers and groups with different rates of disease progression from more chronic (Grade A) to more aggressive (Grade C), in order to assess whether there may be benefit to adjunctive antibiotics targeted to specific populations.

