12.4 Final Analysis Plan

Analysis Population: All analyses will be intent-to-treat, i.e., all participants who provide data at baseline will retain their original assignment regardless of the treatment received. All statistical tests will be evaluated using a two-tailed alpha level of .05 and will express precision using 95% confidence intervals.

Center Effects: The Primary analysis will account for variation between centers using a mixed effects model. The empirical Bayes estimate of center effects resulting from this model will be analyzed to assess the degree of heterogeneity between centers by assessing the magnitude of the variance of the random effects. This assessment will consist of a formal statistical test to determine if the variance of the random effect is greater than zero as well as an assessment of its estimated magnitude. If a clinically meaningful amount of variability between centers is detected, exploratory analyses will be conducted to attempt to identify covariates related to center effects including

geographic information, demographic information, and disease-related information. If these analyses identify meaningful subgroups among the centers, subgroups of sites will be created based on the potential for differential effectiveness. These subgroup analyses will be considered secondary and will be conducted in a manner identical to the primary analysis provided that the subgroups are of sufficient size to merit such an analysis. The specific data related to the characteristics of these subgroups, should they prove to exist, will be reported separately.

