Key Subgroup Analyses & Analyses by Sex, Race and Ethnicity: In order to determine whether any key differences exist by age, sex, or race and ethnicity, analyses of each outcome will be conducted to assess if differences in the intervention effect are to be expected. For our regression analyses, this will take the form of the addition of an interaction term between treatment and subgroup, with a significant p-value suggesting a statistically meaningful difference between the effects experienced by the subgroups. Any significant differences will be examined to determine whether they are of a clinically significant magnitude and comparison of intervention effects will be achieved by reporting intervention effects and their confidence intervals separately for each sex and

for each race/ethnicity group. Further, the raw data will be summarized using boxplots (continuous) or bar charts (binary), stratified by subgroup to visually represent key differences should any be found. These analyses are supported by our randomization scheme which should result in relative balance of treatment assignment across subgroups resulting in unbiased effect estimates.

We will also perform secondary evaluations of the primary outcome measure to assess whether there is effect modification based on age and periodontitis stage and grade, which are key variables associates with periodontitis.

The analysis will consider the following variables:

- Race/ethnicity: non-Hispanic White, non-Hispanic Black, Mexican American, Other Hispanic, Other Race
- Age: continuous variable
- Sex: male or female
- Periodontitis Stage: II, III
- Periodontitis Grade: A, B, C

To test these potential moderators, we will adapt the model described for the primary outcome to include the moderator and product of the moderator and arm in the third level of the model for predicting all level 1 terms. A significant omnibus test based on a contrast would provide support for effect modification. We will probe the nature of any significant interaction by examining the pairwise differences in differences of the change (i.e., moderator X arm X time) and by plotting these values to facilitate interpretation.

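### About 20 treatment-by-subgroup tests are each read at two-sided 0.05 as pointing to effect modification, and nothing in Section 12.4 controls error across them

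*Protocol*

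**What the plan says.** Section 12.4 sets one level for everything: "All statistical tests will be evaluated using a two-tailed alpha level of .05". Its subgroup part has two strands.

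- Demographic factors on all outcomes: "In order to determine whether any key differences exist by age, sex, or race and ethnicity, analyses of each outcome will be conducted". The method is an added treatment-by-subgroup term, "with a significant p-value suggesting a statistically meaningful difference between the effects experienced by the subgroups". Significant differences are then examined for clinical magnitude, and effects with confidence intervals are reported separately by sex and by race/ethnicity.
- Disease-related modifiers of PD: "We will also perform secondary evaluations of the primary outcome measure", the purpose being "to assess whether there is effect modification based on age and periodontitis stage and grade". Here "A significant omnibus test based on a contrast would provide support for effect modification", and pairwise differences are probed only after a significant interaction.

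The stage, grade and age analyses are called secondary. None of the analyses is called exploratory, and none is ranked above another. The section's one statement on multiplicity declines adjustment for the secondary outcome measures, on the ground that they characterise the primary effect. It does not speak of interaction tests.

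The purpose appears earlier. Section 2.1 hopes that "guidelines may be established with tailored indications for their use". Section 2.2 plans effect modification analyses, with smoking and grade as examples, "in order to assess whether there may be benefit to adjunctive antibiotics targeted to specific populations".

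**The concern.** Testing many modifiers is not the problem; the stated reading of a significant result is. The protocol fixes both the level (0.05 for each test) and the interpretation (support for effect modification), and applies them to a large set of tests without saying how many there are or how much weight one positive result carries.

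The stake is what the trial may conclude about who benefits. A chance finding that passes 0.05 would meet the protocol's own rule for effect modification, in a trial that hopes to inform tailored use of antibiotics. Section 2.1 faults earlier trials for lacking power on patient- and disease-related factors, yet Section 12.2 sizes this trial only for the overall 0.2 mm effect. Many chances of a false signal and little power for a true one make a single significant interaction hard to interpret.

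**Working it through.** The protocol states no family-wise error rate for these tests, so there is no figure to reproduce.

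**Count of tests**
- Outcomes in Section 12.4: PD, clinical attachment level, OHIP-5, bleeding on probing, residual disease, remission = 6.
- Age, sex and race/ethnicity on each: 3 × 6 = 18.
- Stage and grade on PD (age is already counted): 2.
- Total: 18 + 2 = 20, with one omnibus test per modifier and outcome.

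This is not a ceiling. Remission is analysed separately at 6 weeks and 12 months, which would add 3 tests (23). The data-driven centre subgroups in Section 12.4 are not counted either.

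**Chance of at least one significant interaction if no modifier is real**

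For k independent tests at 0.05 the chance is 1 − 0.95^k.
- All 20: 1 − 0.95^20 = 0.64, with 20 × 0.05 = 1.0 false positive expected.
- Five listed modifiers on PD only: 1 − 0.95^5 = 0.23.
- Age, stage and grade on PD only: 1 − 0.95^3 = 0.14.

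The outcomes are correlated, and two of them are derived from PD, so 0.64 is too high for the full set. The protocol gives no correlation, so a range was simulated: 200,000 draws with no true modification and independent modifiers. Chi-square tests had 1, 1 and 4 degrees of freedom for age, sex and race/ethnicity on six equally correlated outcomes, and 1 and 2 for stage and grade on PD.

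| Assumed outcome correlation | Chance of at least one |
|---|---|
| 0 | 0.64 |
| 0.3 | 0.61 |
| 0.5 | 0.55 |
| 0.7 | 0.48 |
| 0.8 | 0.43 |
| 0.9 | 0.36 |

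**Power for a real modifier**

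Section 12.2 gives 90% power for a 0.2 mm main effect with 220 per arm. The simulation behind it cannot be rebuilt from the document, so the 90% is taken as stated. The expected z-value of the main effect is then 1.96 + 1.28 = 3.24.

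Split the sample into fractions f and 1 − f. The variance of the difference between the two subgroup effects is the main-effect variance divided by f(1 − f). For a difference of 0.2 mm the expected z-value is 3.24 × √(f(1 − f)).
- f = 0.5: 3.24 × 0.5 = 1.62, power about 0.37.
- f = 0.2: 3.24 × 0.4 = 1.30, power about 0.25.

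**Do the restraints help across tests?** The omnibus gate limits pairwise follow-up within one modifier; it does not limit how many omnibus tests are read at 0.05. The magnitude check comes after significance and has no threshold, so its effect on the error rate cannot be stated.

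**The case against.** The strongest reply is that subgroup tests are customarily unadjusted, that their labelling is often left to the statistical analysis plan (listed as a supplement but not shown), and that effect modification is in neither the hypotheses of Section 12.1 nor the objectives of Section 3. On that view the protocol makes no confirmatory modifier claim and nothing needs controlling. Part of this stands: the lack of an adjustment is not in itself an error, and formal control of all 20 tests is not required. But the point does not rest on silence. The protocol states the level and how a significant result will be read, and leaving subgroup tests unadjusted is acceptable when they are labelled as hypothesis-generating, which these are not.

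Stronger readings are tempting, and the text does not carry them:

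- A reader might infer that a 5% family-wise rate is promised and broken. The 0.05 is a per-test level; no family-wise rate is stated.
- A reader might infer that all 20 tests are meant to set indications. Section 2.2 names smoking and grade as examples, and Section 2.1 speaks generally of person- and disease-related characteristics. Nothing says that, for instance, a race-by-OHIP-5 interaction would set an indication. Age, stage and grade on PD come closest to the targeting aim, and there the figure is 14%.
- A reader might infer that significance alone settles the matter. The protocol's wording is that a difference is suggested and is statistically meaningful, and a clinical check follows for the demographic factors.
- A reader might infer that one modifier, such as grade, must be made confirmatory. Given the low interaction power, that is a debatable trade-off rather than a correction.

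**Conclusion.** The point holds as an issue of interpretation. With no true modifier, the rule in Section 12.4 yields at least one significant interaction with probability 64% if the 20 tests are independent, and 61% to 36% if outcome correlations are 0.3 to 0.9. Those correlations are assumptions, as is independence between modifiers. For narrower families on PD the figure is 23% (five modifiers) or 14% (age, stage, grade); related modifiers, such as stage and grade, could make these somewhat lower. Power for a 0.2 mm difference in effect is about 37% at best for two subgroups, if the stated 90% for the main effect is right.

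A lone p < 0.05 among these tests is thus weak support for effect modification, and the protocol should not say otherwise. The primary and secondary treatment comparisons are untouched, and the text does not show that a false modifier would become an indication.

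**What to change.** In Section 12.4, keep every planned subgroup analysis and replace the rule that a significant interaction supports effect modification. State instead that all treatment-by-subgroup tests and pairwise probing are unadjusted and hypothesis-generating; that they will be reported as estimates with 95% confidence intervals, together with the number of tests done; and that no targeted indication will be concluded from them alone.

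If the sponsor wants a formal modifier claim, confine it to the listed modifiers on PD and apply Holm across them. With all five, the smallest p-value would be compared with 0.05/5 = 0.01.

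The cost is wording only. The downside is that fewer subgroup results may be called significant, and a formal claim under Holm would have less power than the 37% above.

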Step 1: Identify periodontal patients who need to receive a minimum of two quadrants of SRP for periodontal treatment.

Step 2: Evaluate medical history (ASA status) and age inclusion requirements.

Step 3: Confirm that the rest of the eligibility criteria are met, via an electronic screening questionnaire, and as per the screening table below.

Patient participant eligibility Criteria

- At least 40 years of age
- ASA Class I or II
- ≥ 20 teeth, excluding third molars
- Needs periodontal care for Generalized stage II-III, Grade A-C periodontitis
- Indicated to receive SRP in a minimum of 2 quadrants with CDT code 4341
- If diabetic, HbA1c is ≤ 10%
- Willing and able to provide informed consent

- Is NOT currently pregnant or breastfeeding
- Does NOT have a known drug allergy to antibiotic or anesthetics
- No systemic antibiotics within the last 3 months
- No medical condition that requires antibiotic prophylaxis prior to receiving dental treatment

Patient participant Retention: We have estimated for 20% attrition at 12 months. Because the primary endpoint occurs 12 months following treatment and because periodontal patients are usually lifetime patients where maintenance visits are an integral part of periodontitis management, we believe the attrition rate is reasonable. To minimize loss to follow-up, we will work with the study management team at the NCC and regional Node staff to increase retention including study visit reminders to practitioners and patient participants.

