Given the complexity of the correlation structure present in periodontal PD data, the variability in the number of probing sites a given patient participant presents with, and the variability of the correlation in sites depending on which teeth are present, a custom simulation was conducted to further explore the power of this design. In the simulation, patient participants are added to the study with a random number of existing teeth ranging from twenty to twenty-eight, with anterior teeth being added with greater probability than posterior teeth. In order to assign baseline PDs, a correlation structure was constructed in which sites on the same teeth are more highly correlated with each other and sites on different teeth are assigned a correlation based on the distance between them. Simulated baseline PDs are then added with an average depth of 4.5 mm. Similarly changes from baseline were simulated using a similar correlation structure with an average change of 0.3 mm being assumed for the placebo group, a 0.5mm in the AMXM group), and a standard deviation of 1 mm for both groups. This difference of 0.2 mm was chosen as it was determined to be a small but clinically meaningful difference. This synthetic data was then analyzed using the hierarchical model described in section 12.4. The simulation suggested that a sample size of N=220 per arm would be sufficient to achieve 90% power for detecting an average reduction of PD=0.2 mm. Sensitivity analyses were conducted which suggested that by choosing to design the study to a relatively high power of 90%, the design is likely to have adequate power of >80% even if the observed correlation in the study, observed average number of teeth remaining, or the positioning of remaining teeth deviate from that which was included in our initial simulation by a moderate amount. After accounting for a potential dropout rate of 20% and to distribute an even number of patient participants across thirty-four practitioners, the final total sample size would be N=544 or 272 per arm.

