Analysis of Secondary Measures: The analysis of all secondary outcome measures will use similar hierarchical generalized linear models to those described in the primary analysis above. Analyses of all secondary measures enhance and further characterize any effect demonstrated by the primary endpoint as opposed to alternative efficacy measures. Therefore no adjustments for multiple comparisons are necessary nor planned.

For continuous outcome measures of CAL and OHIP-5 we will use the same analytical framework described for the primary outcome, consisting of a mixed effects linear model with random effects for site, patient and provider and fixed effects for time (indicators for 6-week, 12 months) and treatment including a treatment by time interaction. Significance of either interaction term will represent a difference between the treatment and control arm at that timepoint, with the 6-week time representing efficacy and the 12-month time representing long-term efficacy/durability. No transformation of these variables is likely to be necessary.

For the secondary binary outcomes of BOP and the presence of residual disease (tooth level), we will use the generalized extension of the HLM using a logit link and binomial family (aka multilevel logistic regression, random coefficients logistic regression). The terms included in the model will be identical to that described for the continuous outcomes above.

The secondary outcome of remission (participant level) differs from the others in that it is measured at the person level and that the model is not longitudinal given that there is no variability at baseline (i.e., all participants at baseline meet the criteria of this outcome as it is part of the inclusion criteria for participation). Thus, outcome will be evaluated using mixed effects logistic regression, with a random effect for provider and a fixed effect for treatment assignment. This will be conducted separately at reevaluation (6 weeks) and final study visit (12 months). A significant and positive term for arm would indicate an effect of the treatment.

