Sensitivity of the analysis to model misspecification and potential site (provider) effects will be investigated by assessing the cluster-bootstrap stability of the analysis. Any deviations impacting performance will be mitigated by modification of the primary analysis potentially to an approach utilizing the Huber-White sandwich estimator for the variance.

Missing data

For all patient participants, we will attempt to gather follow-up information and reasons for dropout regardless of protocol completion and censor at the point of drop out. PBRN studies routinely attempt to collect reasons for dropout. We will compare baseline data between those with and without missing data and examine whether there are variables that are related to missingness. For each independent variable in the data set, the degree of missingness will be assessed. For key independent variables (demographics, and variables directly relevant to the analyses outlined above), variables with missingness will be dealt with using multiple (greater than or equal to 10) imputation by

chained equations and an appropriate variance will be derived using Rubin's rules (Azur et al. 2011).

Missing outcome variables will not be imputed for analysis. If for a given outcome variable less than 5% of the observations are missing, the missing observations will be dropped. If more than 5% of the outcome variables are missing and the study is positive (demonstrates a benefit for the treatment group over the control), subsequent tipping point analyses will be conducted to determine the potential influence of the missingness on the analysis. Tipping point analyses are used to determine how contrary to the observed data the missing data would need to be in order to reverse the findings of the study. This analysis will be conducted by fitting a predictive model to the observed study data and then using a modified version of that model to impute missing outcomes under progressively increased pessimism until the positive effect observed in the study is countered. This gives the reader an idea of how extremely contrary the missing outcomes would need to be in order to have been influential.

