15.3 Informed Consent Process

Informed consent is a process that is initiated prior to the individual agreeing to participate in the study and continues throughout study participation. Extensive discussion of risks and possible benefits of study participation will be provided to patient participants and their families, if applicable. A consent form describing in detail the study procedures and risks will be given to the patient participant. Consent forms will be IRBapproved, and each patient participant is required to read and review the document or have the document read to him or her. The practitioner or designee will explain the research study to the patient participant and answer any questions that may arise. The patient participant will sign the informed consent document prior to any study-related assessments or procedures. Patient participants will be given the opportunity to discuss the study with their surrogates or think about it prior to agreeing to participate. They may withdraw at any time throughout the course of the study. A copy of the signed informed consent document will be given to patient participants for their records. The rights and welfare of the patient participants will be protected by emphasizing to them that the quality of their clinical care will not be adversely affected if they decline to participate in this study. No further data collection will occur for research purposes; any data collected prior to withdrawal will be used for missing data imputation.

The consent process will be documented in the clinical or research record.

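### The 12-month remission model is an observed-case analysis that leaves unused the 6-week count of later dropouts, and Section 15.3 conflicts on its face with the rule against imputing outcomes

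*Protocol*

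**What the plan says.** - **Remission model (Section 12.4, secondary measures).** Remission is a participant-level yes/no outcome: at most 4 sites with PD of 5 mm or more. It gets a mixed logistic regression with a provider random effect and a fixed effect for arm. On timing: "This will be conducted separately at reevaluation (6 weeks) and final study visit (12 months"). The reason given for not using a longitudinal model is that the outcome does not vary at baseline.
- **Missing outcomes (Section 12.4, missing data).** "Missing outcome variables will not be imputed for analysis". Below 5% missing, the observations are dropped. Above 5%, a tipping-point analysis is added, but only if the study shows a benefit.
- **Analysis population (Section 12.4).** "All analyses will be intent-to-treat, i.e., all participants who provide data at baseline will retain their original assignment".
- **Data from before withdrawal.** Sections 5.5.2 and 7.6 say they go into the intention-to-treat analysis. Section 15.3 says "any data collected prior to withdrawal will be used for missing data imputation", without naming the variables.
- **Expected loss (Section 5.3).** "We have estimated for 20% attrition at 12 months". Section 12.2 uses the same 20% for the sample size.

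**The concern.** PD, CAL, BoP, residual diseased sites and OHIP-5 are analysed in longitudinal mixed models, so a participant who leaves after re-evaluation still contributes the earlier visits. Remission is the exception. With two unlinked models and no imputation, the 12-month model sees only those who attend at 12 months. Sections 5.5.2 and 7.6 promise that data from before withdrawal will be used, but the 12-month remission model has no place for them. The absence of variation at baseline explains why the baseline visit is left out. It does not explain why the 6-week and 12-month results are not connected.

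At stake is the participant-level, treat-to-target result at the later time point. If the people who leave differ in their 6-week response, and differ in another way in the other arm, the observed-case comparison is shifted, and the collected data that could correct it are not used. A reader also cannot tell from Sections 12.4 and 15.3 together whether missing outcomes are imputed.

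**Working it through.** **1. The plan's own figure.** Section 12.2 starts from 220 evaluable per arm and allows for 20% dropout. 220 / (1 − 0.20) = 275 per arm, against the stated 272 (34 × 16 = 544 in total). That agrees within about 1%, and Section 12.2 says the total was also chosen to spread evenly over 34 practitioners. No rate, power or sample size is stated for remission.

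**2. How many leave the 12-month model.** 0.20 × 544 = 108.8, about 109 participants or 54 per arm. This leaves 0.80 × 272 = 217.6 per arm. The 20% is four times the 5% threshold in Section 12.4.

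**3. Effect on the arm comparison.** The inputs below are assumptions, because the documents give none of them:
- remission 45% (AMXM) and 35% (placebo), the same at 6 weeks and 12 months;
- a bivariate normal latent variable linking the two visits, correlation 0.6 or 0.8;
- dropout before 12 months that depends on 6-week remission status, with every participant having a 6-week count;
- 272 per arm, provider effect ignored.

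For one arm, let p6 be the 6-week remission rate, P11 the probability of remission at both visits, P01 the probability of remission at 12 months only, and dR and dN the dropout in 6-week remitters and non-remitters. The observed 12-month rate is

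[(1 − dR) × P11 + (1 − dN) × P01] / [(1 − dR) × p6 + (1 − dN) × (1 − p6)].

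Example: placebo, correlation 0.6, dR = 0.10, dN = 0.30. P11 = 0.2138 and P01 = 0.35 − 0.2138 = 0.1362. The numerator is 0.90 × 0.2138 + 0.70 × 0.1362 = 0.2878. The denominator is 0.90 × 0.35 + 0.70 × 0.65 = 0.77. The observed rate is 0.374 instead of 0.350. With a flat 20% in AMXM (0.450 unchanged), the risk difference is 0.076 instead of 0.100.

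| Dropout in non-remitters / remitters | Arm affected | Observed risk difference, correlation 0.6 / 0.8 (true 10 points) | Shift in points |
|---|---|---|---|
| 30% / 10% | placebo only | 7.6 / 6.6 | −2.4 / −3.4 |
| 30% / 10% | AMXM only | 12.6 / 13.7 | +2.6 / +3.7 |
| 25% / 15% | placebo only | 8.8 / 8.3 | −1.2 / −1.7 |
| 25% / 15% | AMXM only | 11.3 / 11.8 | +1.3 / +1.8 |
| 30% / 10% | both arms alike | 10.2 / 10.2 | +0.2 / +0.25 |

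The unaffected arm has a flat 20%. The standard error of the risk difference is 4.7 to 4.8 points.

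**4. False-positive rate.** Take 40% remission in both arms and selective dropout in one. With 30%/10% the shift is 2.5 to 3.6 points, the standard error about 4.75 points, and two-sided rejection at 0.05 is 8.2% to 11.8%. With 25%/15% it is 5.8% to 6.6%.

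**5. Cross-check with a simpler link.** Assume 12-month remission of 75% in 6-week remitters and 15% in non-remitters, 6-week remission 35% in placebo, and placebo dropout of 7% in remitters and 27% in non-remitters (20% overall).
- True placebo rate: 0.35 × 0.75 + 0.65 × 0.15 = 0.360.
- Observed: (0.35 × 0.93 × 0.75 + 0.65 × 0.73 × 0.15) / (0.35 × 0.93 + 0.65 × 0.73) = 0.315 / 0.800 = 0.394.

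With non-selective dropout in AMXM, the risk difference shifts by −3.4 points. The size is similar.

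**The case against.** **Are these three incompatible populations?** A reader might infer that from setting Section 12.4's intention-to-treat statement, its rule against imputing outcomes and Section 15.3 side by side. The text does not support it. The intention-to-treat statement governs which arm a person is counted in and does not promise everyone a 12-month value. The other two are missing-data rules, and neither names remission. Section 15.3 is a consent section, and its sentence could refer to the chained-equation imputation of independent variables or to the imputation inside the tipping-point analysis. What stands is a conflict on the face of the wording, because Section 15.3 makes no such restriction.

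**Does 20% attrition by itself bias the comparison?** No. When both arms share the mechanism, the shift is at most 0.25 points. The documents give no figure for dropout that differs by arm, and some features speak against it: participants and practitioners are masked, those who stop the drug stay enrolled (Section 5.5.2), and Section 5.3 expects long-term patients. That stands. It does not rule the mechanism out, since only one arm receives active drug and nausea is an expected event (Section 9.3.2).

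**Do all 109 have an unused 6-week count?** No. Some will leave before re-evaluation, for example those withdrawn under the 30-day rule for the second baseline visit. The recoverable share is lower and is not given. The 6-week results themselves are analysed, in the 6-week model.

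**Is there no safeguard?** There is. Section 12.4 compares baseline data by missingness, looks for variables related to missingness, and plans a tipping-point analysis. But the last runs only after a positive result, so it would not run if selective loss hid a benefit, and it does not correct the estimate.

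**Stakes.** Remission is a secondary outcome, and the primary PD model does use a dropout's earlier visits. That limits the weight of the point.

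**Conclusion.** The point holds as a cheap improvement. As written, 12-month remission is an observed-case analysis. It loses about 109 of 544 participants at the planned attrition and cannot use the 6-week count of those who leave after re-evaluation, contrary to what Sections 5.5.2 and 7.6 say about data from before withdrawal. Sections 12.4 and 15.3 need to be reconciled.

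The possible bias is conditional. It is material only if dropout depends on 6-week response differently by arm: 2.4 to 3.7 points (roughly 0.5 to 0.8 of a standard error) and a false-positive rate of 8% to 12% under strong selection in one arm, and 1.2 to 1.8 points under milder selection. The remission rates, the correlation and the dropout patterns are all assumptions. The documents neither show nor exclude such dropout. The shifts are also computed as if every participant had a 6-week count, so they do not show how much of the loss imputation could recover.

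**What to change.** 1. State one missing-outcome rule in Section 12.4, and bring Sections 5.5.2, 7.6 and 15.3 into line with it, saying which variables are imputed.
2. For 12-month remission, multiply impute the missing number of sites with PD of 5 mm or more from arm, practitioner, baseline count and, where available, 6-week count. Derive remission in each imputed data set, fit the planned mixed logistic model, and combine with Rubin's rules.
3. Keep the observed-case analysis as a sensitivity analysis.
4. Run the tipping-point analysis whatever the result.

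A joint logistic model of both visits with participant intercepts should not be treated as an equivalent route, because it estimates a participant-conditional odds ratio. For 45% against 35%, the odds ratio across participants is (0.45/0.55) / (0.35/0.65) = 1.52. The conditional one is about 2.0 with an intercept standard deviation of 2, and about 3.1 with 4.

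The cost is protocol wording and a little more analysis. No new data are needed, and chained-equation imputation with Rubin's rules is already planned for independent variables. The price is a missing-at-random assumption given the imputation variables, including the baseline and 6-week counts. It is weaker than what the observed-case model needs, but it cannot be verified, which is why step 4 should not depend on a positive result.
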